16.9. NICOTINE USE

Nicotine use is assessed at these study visits: Visit 1 and Visit 10. Nicotine use data will be summarized descriptively by treatment group and visit.

For each nicotine type, the amount being used at Week 8/Visit 10 and LOCF in comparison with the amount being used at Baseline will be classified as "increased", "decreased", or "unchanged" for every subject, based on the reported amount used in a given period. If a subject quit using a particular type of nicotine since Baseline, the amount used for that nicotine type will be classified as "decreased". If a subject newly started or restarted using a particular type of nicotine since Baseline, the amount used for that nicotine type will be classified as "increased".

Then for subjects whose changes in amount for all nicotine types between Baseline and each scheduled post-Baseline visit (Week 8/Visit 10 and LOCF) are not in opposite directions, a subject's overall nicotine consumption at each scheduled post-Baseline visit in comparison with Baseline will be classified as "increased", "decreased", or "unchanged" based on the following:

- If the change in amount for each nicotine type is either "increased" or "unchanged", the subject's overall consumption will be classified as "increased".
- If the change in amount for each nicotine type is either "decreased" or "unchanged", the subject's overall consumption will be classified as "decreased".

Document: PPD

Author: PPD

Version Number:

1.0

Version Date:

06MAY2024

- If the change in amount for all nicotine types is “unchanged”, the subject’s overall consumption will be classified as “unchanged”.

The number and percentage of subjects in each overall consumption amount change category will be summarized by treatment group.

In addition, for subjects who reported using “Cigarettes” at either Baseline or each scheduled post-Baseline visit (Week 8/Visit 10 and LOCF) or at both time points, the number of cigarettes used per day will be derived for both time points. The following conversion will be applied if necessary:

- Amount: 1 Pack = 20 Cigarettes.
- Time period: 1 Week = 7 Days; 1 Month = 30 Days.

The amount of cigarette used per day and the change from Baseline values will be summarized by treatment group and visit.

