15.3.6.2. Nicotine Use Information

Nicotine use data will be summarized descriptively at Baseline and Week 8 (end of treatment [EOT]/early termination [ET]). For each nicotine type, the amount being used at each visit in comparison with the amount being used at Baseline will be classified as "increased", "decreased", or "unchanged" for every subject, based on the reported amount used in a given period.

- Then for subjects whose changes in amount for all nicotine types between Baseline and Week 8 (end of treatment [EOT]/early termination [ET]) are not in opposite directions, a subject's overall nicotine consumption at each scheduled post-Baseline visit in comparison with Baseline will be classified as "increased", "decreased", or "unchanged".

The number and percentage of subjects in each overall consumption amount change category will be summarized.

In addition, for subjects who reported using "Cigarettes" at either Baseline or each scheduled post-Baseline visit or at both time points, the amount of cigarette used per day and the change from Baseline values will be summarized by visit.

Further details regarding the specifics of this analysis will be described in the SAP.

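### SAP 16.9: the three overall nicotine-change rules overlap, so a subject with no change meets all three and no precedence is stated

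*SAP*

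**What the plan says.** Nicotine use at Baseline and Week 8 is one of the 'other' endpoints (Protocol 6.3, SAP 2.2.3). Protocol 15.3.6.2 names three overall categories, 'increased', 'decreased' and 'unchanged', without a derivation, and defers to the SAP: "Further details regarding the specifics of this analysis will be described in the SAP".

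SAP 16.9 works in two stages.

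- **By type.** "For each nicotine type, the amount being used at Week 8/Visit 10 and LOCF in comparison with the amount being used at Baseline will be" classed as increased, decreased or unchanged. Quitting a type counts as a decrease; starting or restarting one counts as an increase.
- **Overall.** The overall step is limited to subjects whose changes across types "are not in opposite directions, a subject's overall nicotine consumption at each scheduled post-Baseline visit in comparison with Baseline will be classified as" one of the three labels. The label comes from three bullets:
  - Rule 1 gives 'increased': "If the change in amount for each nicotine type is either 'increased' or 'unchanged".
  - Rule 2 gives 'decreased': "If the change in amount for each nicotine type is either 'decreased' or 'unchanged".
  - Rule 3 gives 'unchanged': "If the change in amount for all nicotine types is" 'unchanged'.

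The result goes into a table: "The number and percentage of subjects in each overall consumption amount change category will be summarized by treatment group".

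The bullets are unnumbered. Nothing in the section says that they are to be tried in order, that the first match ends the search, or that a later rule overrides an earlier one.

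**The concern.** A classification with three exclusive labels needs rules that pick out exactly one label per subject. Here the word 'unchanged' sits inside the conditions for both 'increased' and 'decreased', with no requirement that at least one type moved. A subject who reports the same amount of every product at both visits therefore qualifies for all three labels.

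That subject is the reference case of the table. Two programmers working from the same three bullets could produce different tables, and one version would report stable users as having increased their use after the switch. Elsewhere the SAP takes care to settle such cases: an overriding rule for medication timing (Appendix 2), a tie category for modal dose (14.1), a worst-case rule for adverse event severity and relationship (17.3), and QTc change bands written so that they cannot overlap (17.5.1). The nicotine rules have no such provision.

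**Working it through.** The documents give no figure to reproduce on this point. The check is to apply the three conditions literally to every possible pattern.

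**Inputs, all from SAP 16.9.** Each type is increased, decreased or unchanged. A subject with one type increased and another decreased is not eligible. Rules 1 to 3 are as described above, with no precedence.

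**Step 1: which rules each kind of pattern meets.** 'First match' means IF / ELSE IF in the listed order. 'Overwrite' means successive IF statements in the same order, each replacing the last. 'Amended' adds the requirement of at least one increased type to rule 1 and at least one decreased type to rule 2.

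| Pattern across types | Rule 1 | Rule 2 | Rule 3 | First match | Overwrite | Amended |
|---|---|---|---|---|---|---|
| At least one increased, none decreased | yes | no | no | increased | increased | increased |
| At least one decreased, none increased | no | yes | no | decreased | decreased | decreased |
| Every type unchanged | yes | yes | yes | **increased** | unchanged | unchanged |
| Some increased, some decreased | not eligible | – | – | – | – | – |

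**Step 2: how many patterns are affected.** With k types, 2^k patterns contain no decrease and 2^k contain no increase. The all-unchanged pattern is in both sets, so the number of eligible patterns is 2 × 2^k − 1.

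- k = 1: 2 × 2 − 1 = 3
- k = 2: 2 × 4 − 1 = 7
- k = 3: 2 × 8 − 1 = 15

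Full enumeration for one, two and three types confirms these counts. In each case exactly one pattern, all unchanged, meets more than one rule, and it meets all three. Overwriting assignments agree with the amended rules on every pattern. The amended rules give every pattern exactly one label.

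**Step 3: size of the error.** Let i, d and u be the true shares of eligible subjects who increased, decreased and did not change, with i + d + u = 1.

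| Coding | 'Increased' row | 'Decreased' row | 'Unchanged' row |
|---|---|---|---|
| First match | i + u | d | 0 |
| Overwrite | i | d | u |
| Three independent flags | i + u | d + u | u |

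First match overstates 'increased' by u; overwriting has no error. Independent flags overstate both 'increased' and 'decreased' by u, and the rows add to 1 + 2u, which would be noticed.

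The documents give no value for u. As an illustration only, assume u = 60% and i = d = 20%. First match then shows 80% increased, 20% decreased and 0% unchanged. Overwriting shows 20%, 20% and 60%. For assumed values of u from 40% to 80%, the first-match error is 40 to 80 percentage points and the overwriting error stays at zero.

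**The case against.** The strongest reply is that the intent is plain. SAP 16.9 promises three categories and gives the all-unchanged case its own, more specific rule. A reading that makes that rule unreachable, leaves one category permanently empty, and calls a one-product user unchanged by type but increased overall is not the natural one. A careful programmer would probably get it right. This stands as far as intent goes. It does not remove the overlap: the written conditions still give three labels to one subject, and the correct table then depends on coding style or on the programmer's judgement.

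A reader might infer more: that applying the bullets in their listed order necessarily reports every stable user as 'increased', so that the study would appear to show nicotine use rising after the switch. The documents do not support that. The SAP prescribes no first-match logic, and successive assignments in the same listed order give the right answer. The large overstatement in the illustration repeats an assumed unchanged share under one assumed coding; it is not an expected bias.

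Nor does the overall category carry the whole endpoint. SAP 16.9 also provides a descriptive summary by visit, the change by type, and cigarettes per day with change from Baseline. None of these uses the three rules, and a spurious excess of 'increased' would conflict with them.

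**Conclusion.** The overlap is real and follows from the text alone: read literally, the rules give an all-unchanged subject three labels, and neither SAP 16.9 nor Protocol 15.3.6.2 resolves it. Every other eligible pattern is classified without ambiguity.

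The error in the 'increased' row lies between zero and the whole unchanged share of eligible subjects, depending on coding. The upper end rests on first-match coding, which is an assumption about the program and not something the SAP states.

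The reach is small. One table of one descriptive 'other' endpoint is affected, in a single-group study for which the SAP plans no statistical comparisons (7.1, 7.4). The primary and secondary discontinuation endpoints do not use these rules. This is a minor wording correction, worth making because it is nearly free.

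**What to change.** In SAP 16.9:

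- Reword rule 1: 'increased' if at least one nicotine type increased and none decreased.
- Reword rule 2: 'decreased' if at least one nicotine type decreased and none increased.
- Keep rule 3 for subjects with every type unchanged.

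With these changes every eligible pattern maps to exactly one category, whatever order the rules are coded in. A sentence saying that rule 3 takes precedence would have the same effect, but the rewording is cleaner.

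The cost is two lines of SAP text and about one line of derivation code; no new data are needed. Whether to show subjects with no nicotine use at either visit in a row of their own is an optional presentation choice and is not part of this point.

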16.10. MISSING DATA METHOD

Any individual missing item in any scale will not be imputed.

For derived scores that depend on more than one individual item (e.g., PANSS total score, PANSS subscale scores, PANSS Marder factor scores, PANSS UPSM factor scores and UPSM total factor score, BNSS total score, BNSS subscale scores, MADRS total score), if one or more items are missing at a visit, the derived score will be set to missing. The corresponding change from Baseline value at a given post-Baseline time point will be set to missing if the Baseline derived score is missing or if the derived score at that time point is missing.

For PANSS response, any subject with a missing PANSS total score at Baseline or at any post-Baseline time point will have their PANSS response set to missing for that time point.

For PSP binary variables based on the PSP total score, if the PSP total score is missing at Baseline or at any post-Baseline time point, the affected binary variable will be set to missing.

17. SAFETY OUTCOMES

Unless otherwise specified, the safety analysis and summary tables will include the column SEP-363856 50 to 100 mg/day

All analyses of the safety outcomes will be based on the SAF Population, by treatment group.

Document:	PPD		
Author:	PPD	Version Number:	1.0

Version Date:
06MAY2024

17.1. DISCONTINUATION DUE TO CLINICAL REASONS

Discontinuation for clinical reasons is defined as reasons due to AE or lack of efficacy. AE will follow the definition as in section [17.3](#).

The percentage of subjects who discontinued for clinical reasons will be calculated by a proportion consisting of the number of subjects who experience a discontinuation event due to clinical reasons as the numerator divided by the number of subjects in the safety population as the denominator multiplied by 100 along with a corresponding 95% confidence interval (CI).

The number and percentage of subjects, who discontinued early from the open-label treatment period (including both clinical reasons, ie, discontinued due to an AE or lack of efficacy (primary endpoint) and any reason for discontinuation (secondary endpoint)) will be presented.

The time-to-discontinuation for clinical reasons will be summarized descriptively, (eg, n, median, 25th percentile, 75th percentile, minimum and maximum, and 95% CI on median, where possible).

Time to discontinuation for clinical reasons since first dose of study medication will be plotted using Kaplan-Meier curves for the safety population by treatment group. Probability of remaining on treatment at Day 56, median time to discontinuation, and their 95% confidence intervals will be estimated using the Kaplan-Meier method for the safety population by treatment group.

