13. TERMINATION OF SUBJECT FROM STUDY

13.1. Criteria for Subject Termination

Subjects may be discontinued from study participation / the study drug at any time for any of the following reasons. The possible reasons for termination of study participation / study drug are as follows:

- Adverse event
- Lack of efficacy (specify)
- Lost to follow-up (specify)
- Withdrawal by subject (specify)
- Non-compliance with study drug (specify)
- Protocol deviation (specify)
- Death
- Pregnancy
- Other (specify)

If at any time during the course of the study, in the opinion of the Investigator, the subject may no longer safely participate due to a change in medical status (eg, experiences an AE, becomes pregnant), the subject must be discontinued from the study drug. Subjects discontinued from study drug will be discontinued from the study.

The reason for discontinuation of “Lack of efficacy” should be selected when a subject early terminates from the study because there has been insufficient therapeutic benefit of the study drug (perceived or actual) and the subject’s baseline condition has neither worsened nor improved significantly.

The reason for study drug discontinuation will be recorded on the appropriate CRF. In case of death, the date of death should be captured on the CRF. Subjects who prematurely terminate the study participation will not be replaced.

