15.3.5.1. Primary and Secondary Endpoint Analysis

The primary endpoint is the percentage of subjects who discontinued for clinical reasons, such as due to AE or lack of efficacy. This percentage will be calculated by a proportion consisting of the number of subjects who experience a discontinuation event due to clinical reasons as the numerator divided by the number of subjects in the safety population as the denominator multiplied by 100 along with a corresponding 95% confidence interval (CI).

The secondary endpoint is the percentage of subjects who discontinued for any reason (ie, all cause discontinuation). The percentage will be calculated similarly as that of the primary endpoint along with a corresponding 95% CI.

The number and percentage of subjects, who discontinued early from the open-label treatment period (including both clinical reasons, ie, discontinued due to an AE (primary endpoint) and any reason for discontinuation (secondary endpoint)) will be presented.

As an exploratory analysis, the time-to-discontinuation for both clinical reason and for any reason will be summarized descriptively, (eg, n, median, 25th percentile, 75th percentile, minimum and maximum, and 95% CI on median, where possible) and presented with corresponding Kaplan-Meier plots.

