3.7. CHANGES TO ANALYSIS FROM PROTOCOL

There are no changes to analysis from the protocol.

Document:	PPD		
Author:	PPD	Version Number:	1.0

Version Date: 06MAY2024

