9.1. DERIVATIONS

- Time to discontinuation of the treatment in days.

For the purpose of this analysis, a subject's last dose date will be derived as follows:

- o If a subject's observed last dose date is before or on the date of Study Day 56, the derived last dose date will be set to the observed last dose date.
- o If a subject's observed last dose date is after the date of Study Day 56, the derived last dose date will be set to the date of Study Day 56.

Time to discontinuation (days) = Derived last dose date – First dose date + 1.

The event of interest is the discontinuation of treatment. Subjects who completed the treatment will be censored on the derived last dose date.

Document: PPD

Author: PPD

Version Number:

1.0

Version Date:

06MAY2024

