17.2. DISCONTINUATION DUE TO ANY REASONS

The percentage of subjects who discontinued for any reason (ie, all cause discontinuation). The percentage will be calculated similarly as that of the primary endpoint along with a corresponding 95% CI.

Kaplan-Meier analysis as in section [17.1](#) will be performed for time to discontinuation for any reasons.

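### The Day 56 Kaplan-Meier value for clinical-reason discontinuation is labelled as the probability of remaining on treatment, which it does not estimate, and the handling of subjects who leave for other reasons is not stated

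*SAP*

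**What the plan says.** SAP 17.1 sets the event narrowly: "Discontinuation for clinical reasons is defined as reasons due to AE or lack of efficacy". It then specifies the curve, "Time to discontinuation for clinical reasons since first dose of study medication will be plotted using Kaplan-Meier curves for the safety population by treatment group", and what is read from it: "Probability of remaining on treatment at Day 56, median time to discontinuation, and their 95% confidence intervals will be estimated using the Kaplan-Meier method".

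SAP 17.2 says that the same Kaplan-Meier analysis "will be performed for time to discontinuation for any reasons".

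The only rule for events and censoring is in SAP 9.1: "The event of interest is the discontinuation of treatment. Subjects who completed the treatment will be censored on the derived last dose date". The derived last dose date is capped at Study Day 56. No cause-specific version of this rule is given.

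Protocol 13.1 introduces its list with "The possible reasons for termination of study participation / study drug are as follows" and names nine. Two are clinical in the sense of SAP 17.1. The other seven are loss to follow-up, subject withdrawal, non-compliance, protocol deviation, death, pregnancy and a residual category.

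Protocol 15.3.5.1 sets the status of the analysis: "As an exploratory analysis, the time-to-discontinuation for both clinical reason and for any reason will be summarized descriptively". It asks for descriptive summaries and Kaplan-Meier plots. The Day 56 retention wording appears only in the SAP.

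**The concern.** The label and the event do not match. A subject who withdraws consent in Week 3 has not had a clinical-reason event, but is no longer on treatment. Whatever the clinical-reason curve shows at Day 56, it is not the fraction still taking the drug unless nobody leaves for another reason.

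The handling of other-reason leavers is also left open. They could be censored at last dose, carried event-free to Day 56, treated as competing events or counted as events. Two programmers could follow the text and draw different curves.

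Since 17.2 repeats the analysis for any reason, the SAP attaches one name to two quantities, and the name is right for only one of them. This matters more than usual because the clinical-reason median will almost certainly not be reached at rates of 7.2% or 15%. The Day 56 value is then the main number the curve yields, and retention is what a reader of a switch study looks for.

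**Working it through.** **Inputs from the documents.** Clinical-reason discontinuation c = 15% (planning value) and 7.2% (revised value), planned half-widths 6.4 and 5.1 points, and 101 enrolled, all from SAP 3.4. **Assumed:** the other-reason share o, which the documents do not give; 5% to 20% is used.

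**The plan's own figures.** No Day 56 Kaplan-Meier value is stated. The planned half-widths, used below as a yardstick, do reproduce:
- 1.96 × √(0.15 × 0.85 / 120) = 6.39 points (stated 6.4)
- 1.96 × √(0.072 × 0.928 / 100) = 5.07 points (stated 5.1)

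**Step 1: other-reason leavers censored, constant cause-specific hazards to Day 56.**
- Total cumulative hazard H = −ln(1 − c − o)
- Clinical part Hc = H × c / (c + o)
- Kaplan-Meier value KM = exp(−Hc)
- Share actually on treatment = 1 − c − o

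For c = 7.2% and o = 10%: H = −ln(0.828) = 0.1887; Hc = 0.1887 × 0.072 / 0.172 = 0.0790; KM = 92.40%; on treatment 82.8%; gap 9.60 points.

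| c | o | KM at Day 56 | On treatment | Gap (points) | 1 − KM |
|---|---|---|---|---|---|
| 7.2% | 5% | 92.61% | 87.8% | 4.81 | 7.39% |
| 7.2% | 10% | 92.40% | 82.8% | 9.60 | 7.60% |
| 7.2% | 15% | 92.18% | 77.8% | 14.38 | 7.82% |
| 7.2% | 20% | 91.94% | 72.8% | 19.14 | 8.06% |
| 15% | 5% | 84.59% | 80% | 4.59 | 15.41% |
| 15% | 10% | 84.15% | 75% | 9.15 | 15.85% |
| 15% | 15% | 83.67% | 70% | 13.67 | 16.33% |
| 15% | 20% | 83.14% | 65% | 18.14 | 16.86% |

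**Step 2: drop the constant-hazard assumption.** Take n = 101, 7 clinical exits (about 7%) and an assumed 10 other exits. The order of exits bounds the censored estimate:
- all clinical exits first: 1 − 7/101 = 93.07%
- all other exits first: 1 − 7/91 = 92.31%
- both spread evenly over the period: 92.7%

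The share on treatment is 84/101 = 83.2% in every case. With 5, 15 and 20 other exits, the lower bounds are 1 − 7/96 = 92.71%, 1 − 7/86 = 91.86% and 1 − 7/81 = 91.36%, against 88.1%, 78.2% and 73.3% on treatment.

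**Step 3: the alternative readings.** Same example, 7 clinical and 10 other exits:
- other-reason leavers carried event-free to Day 56: 94/101 = 93.1%, still not retention
- every discontinuation counted as an event: 83.2%, which is retention, but this is the 17.2 analysis

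**Step 4: agreement with the primary result.** 1 − KM exceeds the crude clinical proportion by 0.2 to 0.9 points at 7.2%, and by 0.4 to 1.9 points at 15%. At 7.2% this is well inside the 5.1-point half-width. The curve therefore does not conflict with the primary endpoint; the error is in calling its complement retention.

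**The case against.** The strongest objection is that SAP 9.1, read literally, makes every discontinuation an event and censors only completers, so the label would be correct. But the curve in 17.1 would then be identical to the one in 17.2 and would not be a clinical-reason curve. Either the label or the event definition has to give way, and the need to choose between readings shows that the rule is missing.

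Second, SAP 8 refers to output templates that were not available for this review. Titles and footnotes there may be clearer. That is possible, but it does not correct the SAP's own sentence.

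Third, the context limits the harm. The sentence sits under a clinical-reasons heading, the analysis is exploratory, the study has one arm and no tests, and the disposition summaries in SAP 9 show completers and reasons. All of this stands, and it keeps the point below anything touching the main conclusions.

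Fourth, the size of the gap is largely the assumed other-reason rate restated. SAP 3.4 also mentions better retention than predicted, without a figure, so the low end of the range may be the more realistic. That is fair: the figures are illustrations, not forecasts.

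Fifth, a competing-risks estimate would nearly duplicate the primary proportion. It would, so it is optional.

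**Conclusion.** The concern holds. As written, SAP 17.1 gives a retention label to a quantity that is not retention, and no section says how subjects leaving for the seven other reasons enter the clinical-reason curve. On the natural reading (those subjects censored), the value estimates the probability of no clinical-reason discontinuation if nobody left for another reason, under independent censoring.

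The overstatement of retention is close to the other-reason dropout rate: about 5 points at 5% and about 19 points at 20% when clinical discontinuation is 7.2%. It vanishes only if that rate is zero. These sizes rest on the assumed rates; the direction of the error does not.

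The primary and secondary proportions, their confidence intervals and the sample size are unaffected. This should be corrected, but it does not threaten the main result.

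**What to change.** In SAP 9.1 and 17.1:
- Define the clinical-reason event as discontinuation due to adverse event or lack of efficacy.
- State that discontinuation for any other reason is censored on the derived last dose date in the Kaplan-Meier plot, and that completers are censored as now. Say explicitly where a disposition record of death falls, since protocol 13.1 lists it separately from adverse event.
- Label the Day 56 value as the probability of no clinical-reason discontinuation, with other-reason discontinuations censored.
- Reserve the remaining-on-treatment label for the any-reason analysis in 17.2.

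Optionally, add the Day 56 cumulative incidence (Aalen-Johansen) with a 95% CI, treating other-reason exits as competing events. It essentially equals the primary proportion and so ties the time-to-event output to it. If it is added, record it in SAP 3.7, which currently reads "There are no changes to analysis from the protocol".

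The cost is two or three sentences and one relabelled figure, plus one descriptive output and one line in 3.7 if the option is taken. No new data are needed.
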